Number of Participants: It is estimated that up to approximately 60 participants will be enrolled in Part 1. In Part 2, approximately 141 participants will be recruited into Expansion Cohort 2A (~36 participants) and Expansion Cohort 2B (~ 105 participants). Additional tumor-specific cohort(s) and combinations may be added by protocol amendment, based upon emerging pre-clinical data, or clinical data.

Intervention Groups and Duration: In Part 1 of the study, the participants will initially receive GSK3368715 orally. This will include at least one PK/PD cohort and a food effect cohort. The Dose Limiting Toxicity (DLT) period is 21 days, and under protocol amendment 3, there is an addition of a VTE-specific DLT period of 8 (\pm 1) weeks or until study discontinuation whichever occurs sooner. An end of treatment CT image is required if the participant withdraws before the end of the DLT observation period. Alternative dosing schedules and intervention cycles may be investigated. In Part 2, the participants are expected to receive the RP2D established in Part 1. In case of unexpected toxicities, alternative GSK3368715 doses may be explored in Part 2.

The study includes a screening period, an intervention period and follow up. Participants will be screened for eligibility beginning approximately 4 weeks before the start of intervention. Participants with confirmed partial response (PR) or complete response (CR) will be followed for response duration and may be eligible for additional intervention with GSK3368715 at the time of relapse/progression if determined to be deriving clinical benefit in the opinion of the investigator and with approval from the study Medical Monitor.

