4.1.3. Dose-Limiting Toxicity

All toxicities will be graded using National Cancer Institute – Common Toxicity Criteria for Adverse Events (NCI-CTCAE), version 5.

An AE is considered to be a dose-limiting toxicity (DLT) if the event is considered by the investigator to be clinically relevant and attributed (definitely, probably or possibly) to the study intervention during the first 21 days of intervention and meets at least one of the criteria listed in [Table 6](#).

In addition, there are clear VTE DLT criteria:

- Upon re-initiation of enrolment under Protocol Amendment 3, any cohort in Part 1 with two (2) grade 2 venous thromboembolism (VTE) that requires systemic anticoagulation or \geq grade 3 VTE in up to 6 participants will be considered not cleared and enrolment at this dose level and higher dose levels will be permanently stopped.
- Upon re-initiation of enrolment under Protocol Amendment 3, any cohort in Part 1 with ≥ 3 grade 2 venous thromboembolism (VTE) that requires systemic anticoagulation or Grade ≥ 3 VTEs out of up to 10 participants will be considered not cleared and enrolment at this dose level and higher dose levels will be permanently stopped.
- Upon re-initiation of enrolment under Protocol Amendment 3 at 100mg, dose escalation steps will be considered in maximal steps of 50 mg depending on the pharmacodynamic effects and the safety profile observed in previous cohorts, taking into consideration the updated DLT criteria (see [Table 6](#)).
- Grade 2 venous thromboembolism (VTE) that requires systemic anticoagulation or \geq grade 3 VTE, regardless of investigator assessed causality, will be considered a DLT during the first 8 (± 1) weeks or until study discontinuation (e.g., disease progression), whichever occurs sooner.
- An end of treatment CT image is required if the participant withdraws before the end of the VTE DLT observation period ([Table 6](#)).

If an AE is considered related to the underlying disease it is not defined as a DLT.

Table 6 Dose-Limiting Toxicity Criteria

DLT criteria for Non-hematologic Toxicity	
AST or ALT	
 • Grade 3 • Grade 4 • ALT \geq 5xULN • ALT \geq 3xULN persists for \geq 4 weeks • ALT \geq 3xULN and bilirubin \geq 2xULN (>35% direct bilirubin) • ALT \geq 3xULN and INR >1.5, if INR measured • ALT \geq 3xULN associated with symptoms (new or worsening) believed to be related to liver injury or hypersensitivity

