### 3. PLANNED ANALYSES

#### 3.1. Interim Analyses

In Part 1, dose escalation meetings will be held to discuss dose escalation decisions after all patients in each dose cohort complete the DLT evaluation period of the first 21 days of intervention. Once all subjects in the DLT evaluation cohort (approx. 30 in total) have completed the first post baseline disease assessment, progressed or permanently discontinued from study treatment, a RP2D analysis will be conducted.

The Dose Escalation Committee (DEC) evaluated the DL100mg cohort and deemed it safe, but upon review of the cumulative safety, efficacy, PK and PD data, GSK decided that no further enrolment will take place on the study. As a result, all analyses corresponding to Part 2, as well as the Exploratory Objectives for both Part 1 and Part 2, will not be performed. However, all other Part 1 analyses will be performed.

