### 8.2. Adverse Events Analyses

Adverse events analyses including the analysis of adverse events (AEs) and Serious (SAEs) will be based on GSK Core Data Standards.

Dose limiting toxicity (DLT) will also be summarized and listed according to GSK Oncology Data Standards.

AEs will be graded by the investigator according to the National Cancer Institute-Common Toxicity Criteria for Adverse Events (NCI-CTCAE) v5.0. AEs will be coded to the Preferred Term (PT) level using the Medical Dictionary for Regulatory Affairs (MedDRA).

An overview summary of AEs, including counts and percentages of subjects with any AEs leading to dose reductions of GSK3368715 and AEs leading to dose interruptions of GSK3368715 will be produced. Separate listings of fatal serious adverse events (SAEs), non-fatal SAEs, reasons for considering as a SAE, AEs leading to permanent discontinuation of GSK3368715, AEs leading to dose interruptions of GSK3368715, AEs leading to dose reductions of GSK3368715, will be produced.

Non-serious AEs that occurred in strictly 5% or more subjects (no rounding for the percentage will be used in terms of 5% threshold, e.g. events with 4.9% incidence rate should not be included in this table) will be summarized by PT.

A summary of number and percentage of subjects with any AEs by maximum grade will be produced. AEs will be sorted by PT in descending order of total incidence. The summary will use the following algorithms for counting the subject:

- **Preferred term row:** Subjects experiencing the same AE preferred term several times with different grades will only be counted once with the maximum grade.
- **Any event row:** Each subject with at least one AE will be counted only once at the maximum grade no matter how many events they have.

In addition, the frequency and percentage of AEs (all grades) will be summarized and displayed by descending order of total incidence by SOC and PT. In the SOC row, the

number of subjects with multiple events under the same system organ class will be counted once.

A study treatment-related AE is defined as an AE for which the investigator classifies the relationship to study treatment as “Yes”. A worst-case scenario approach will be taken to handle missing relatedness data, i.e. the summary table will include events with the relationship to study treatment as ‘Yes’ or missing. A summary table of study treatment-related AEs by maximum grade will be displayed in descending order of total incidence by PT only.

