## 14.7. Appendix 7: Reporting Standards for Missing Data

### 14.7.1. Premature Withdrawals

| Element | Reporting Detail  |
|---------|---|
| General | 
 
• A participant enrolled in Part 1 will be considered to have completed the study if they are DLT-evaluable, i.e.:               
 
○ they complete screening assessments, at least 21 days of study intervention and the post-intervention follow-up visit, or
 
○ they discontinue study intervention before Day 21 due to drug related toxicity. Participants who discontinue study intervention before day 21 or who received less than 75% of the intended dose in the first 21 days for reasons other than study drug related toxicity are not considered to have completed the study.
 
 
 
• All available data from participants who were withdrawn from the study will be listed and all available planned data will be included in summary tables and figures, unless otherwise specified.
 
 |

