| 3.17.                               | All Treated       | EG2                             | Summary of Change from Baseline in ECG Values by Visit                        | IDSL                     | SAC                |
| Vital Signs                  |                   |                                 |   |                          |                    |
| 3.18.                               | All Treated       | VS1                             | Summary of Change from Baseline in Vital Signs                                | ICH E3                   | SAC                |
| Dose Modifications           |                   |                                 |   |                          |                    |
| 3.19.                               | All Treated       | ODMOD1                          | Summary of Dose Reductions of GSK3368715                                      | ICH E3                   | SAC                |
| 3.20.                               | All Treated       | ODMOD2                          | Summary of Dose Interruptions of GSK3368715                                   | ICH E3                   | SAC                |
| 3.21.                               | All Treated       | ODMOD8                          | Summary of Dose Escalations of GSK3368715                                     | If applicable.           | SAC                |
| Dose Limiting Toxicity (DLT) |                   |                                 |   |                          |                    |
| 3.22.                               | All Treated       | DL1                             | Summary of Dose-Limiting Toxicities during the Determinative Period           | ICH E3                   | SAC                |

| Safety: Tables            |             |                      |  |                   |             |
|---------------------------|-------------|----------------------|--|-------------------|-------------|
| No.                       | Population  | IDSL / Example Shell | Title  | Programming Notes | Deliverable |
| Performance Status |             |                      |  |                   |             |
| 3.23.                     | All Treated | PS1A                 | Summary of ECOG Performance Status                         | ICH E3            | SAC         |

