| 20.   | All Treated       | AE8                         | Listing of Adverse Events Leading to Dose Interruptions of Study Treatment        | ICH E3                   | SAC                |
| 21.   | All Treated       | AE8                         | Listing of Adverse Events Leading to Dose reductions of Study Treatment           | ICH E3                   | SAC                |
| Dose-Limiting Toxicities                     |                   |                             |   |                          |                    |
| 22.   | All Treated       | DL3                         | Listing of Dose-Limiting Toxicities (DLT) During the Determinative Period         |                          | SAC                |

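### Protocol 4.1.3 makes a qualifying VTE a DLT whatever its cause, then exempts disease-related AEs without excepting VTE

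*Protocol*

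**What the plan says.** Protocol 4.1.3 starts from a general definition: a DLT is attributed at least possibly to the study drug, occurs in the first 21 days and meets a Table 6 criterion. It then adds separate VTE criteria under Amendment 3. A Grade 2 VTE needing systemic anticoagulation, or a VTE of Grade 3 or above, "regardless of investigator assessed causality, will be considered a DLT during the first 8" (± 1) weeks, or until study discontinuation if that comes earlier. Straight after the VTE bullets stands an unqualified sentence: "If an AE is considered related to the underlying disease it is not defined as a DLT". The VTE row of Table 6 repeats the grades and the window but is silent on causality. The synopsis agrees that there are two periods: besides the 21 days, "there is an addition of a VTE-specific DLT period of 8" (± 1) weeks.

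SAP 2.3 restates the VTE rule with its causality clause and does not carry the exemption over. SAP 3.1.1 refers to 4.1.3 and Table 6 for VTEs that meet the DLT criteria. On reporting, SAP 8.2 says only: "Dose limiting toxicity (DLT) will also be summarized and listed according to GSK Oncology Data Standards". The planned displays are Table 3.22, "Summary of Dose-Limiting Toxicities during the Determinative Period" (SAP 14.10.5), and Listing 22, "Listing of Dose-Limiting Toxicities (DLT) During the Determinative Period" (SAP 14.10.8). The supplied text does not define the Determinative Period.

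**The concern.** The two rules in 4.1.3 give opposite answers for a qualifying VTE that the investigator attributes to the cancer, and neither says which prevails. That attribution is foreseeable: everyone in Part 1 has an advanced solid tumor, and cancer is the obvious alternative explanation for a clot. The VTE rule was added because more VTEs than expected were seen in the first 19 participants (Protocol 2.3.1). A causality-blind rule that can be undone by a causality judgement does not do what it was written to do.

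The general definition already requires attribution to the drug, so for other toxicities the closing sentence adds little beyond cases of mixed attribution. VTE is the one class where attribution is otherwise irrelevant, so the sentence bites hardest there.

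DLT incidence is a Part 1 primary endpoint (Protocol 3, SAP 2.2), and Table 3.22 and Listing 22 are its final displays. What is at stake is whether such a VTE carries the DLT label and enters the count for its dose.

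**Working it through.** **1. The two rules side by side, for a VTE that meets the grade criterion inside the window**

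| Attributed to | VTE bullet | Closing sentence, read literally |
|---|---|---|
| Study drug | DLT | No effect |
| Neither drug nor cancer | DLT | No effect |
| Cancer | DLT | Not a DLT |

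Only the last row conflicts.

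**2. Effect of one event on the reported rate.** With n participants at a dose, relabelling one participant's event shifts the observed DLT rate by 1/n. SAP 2.3 allows 3 to 12 per dose level, and Protocol 9.2 plans about 10 per PK/PD cohort.

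- n = 12: 1/12 = 8.3 points
- n = 10: 1/10 = 10.0 points
- n = 6: 1/6 = 16.7 points
- n = 3: 1/3 = 33.3 points

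The n = 3 figure is an extreme case. Amendment 3 enrolment restarts in the 100 mg and 50 mg PK/PD cohorts, and SAP 5.1 displays Part 1 by dose level, so 8 to 10 points is the relevant size.

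**3. The cohort-stopping rule is separate.** The stopping bullets in 4.1.3 count VTEs by grade and need for anticoagulation, and Protocol 9.2.1.1 simulates VTE events. Neither uses DLT status or attribution. For the simulated rule (2 or more in up to 6, or 3 or more in 7 to 10), the exact stopping probability at true rate p is

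P(stop) = P(X6 ≥ 2) + P(X6 = 0) × P(X4 ≥ 3) + P(X6 = 1) × P(X4 ≥ 2),

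where X6 is binomial on the first 6 participants and X4 on the next 4. At p = 0.30 this is 0.5798 + 0.1176 × 0.0837 + 0.3025 × 0.3483 = 0.695.

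| True VTE rate | Table 8 (%) | Exact (%) |
|---|---|---|
| 5% | 3.8 | 3.6 |
| 10% | 13.6 | 13.5 |
| 15% | 26.9 | 27.2 |
| 20% | 42.1 | 42.3 |
| 25% | 56.8 | 56.8 |
| 30% | 69.5 | 69.5 |

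All agree within 0.3 points. Table 8 stands with every VTE counted, which is how the rule is written.

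**4. The edge of the window.** Seven, 8 and 9 weeks end on Days 49, 56 and 63. The first scheduled on-treatment chest CT is Week 9 Day 1, which is 8 × 7 + 1 = Day 57. A VTE first seen on that scan lies outside an 8-week cutoff and inside a 9-week one, so a counting rule needs one stated day.

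**The case against.** The strongest reply is that the specific rule governs the general one. Section 4.1.3 sets the VTE criteria apart as an addition to the attribution-based, 21-day definition. If the closing sentence applied to them, a cancer attribution would defeat most of what the causality clause is for. SAP 2.3, which guides the analysis, restates the VTE rule without the exemption. This largely stands: the VTE bullet is the more plausible reading. It does not remove the problem, because investigators work from the protocol, the exemption comes last and is unqualified, and nothing there states the order of precedence.

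A reader might also infer that the SAP will drop VTE DLTs after Day 21, because SAP 3.1 speaks of a "DLT evaluation period of the first 21 days of intervention" and SAP 14.7.1 treats as DLT-evaluable those for whom "they complete screening assessments, at least 21 days of study intervention and the post-intervention follow-up visit" holds. The documents do not show that. SAP 3.1 sets when escalation meetings are held, and SAP 14.7.1 defines study completion. Neither fixes which events count, and SAP 2.3 and 3.1.1 both adopt the VTE rule. The Determinative Period may be defined in display shells DL1 and DL3 or in the GSK Oncology Data Standards, which are not supplied. What stands is that a reader of the SAP alone cannot tell which period the displays use.

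**Conclusion.** The conflict within 4.1.3 is real and minor. Read literally, the closing sentence takes the DLT label from a qualifying VTE attributed to the cancer. The size is 1/n per event in the observed DLT rate at that dose, about 8 to 10 points at n = 12 to 10. This assumes that such an event occurs and that the investigator follows the closing sentence. The documents show no such event and give no rate of cancer attribution.

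A reader might infer that the exemption weakens the VTE stopping rule or invalidates Table 8. It does not, because that rule counts VTEs without reference to DLT status. Nor would any VTE disappear from reporting: VTEs remain in the AE tables and listings. Enrolment is closed and no RP2D analysis will be done (SAP 2.1), so no future dose decision turns on the point. The undefined Determinative Period is a supporting clarification, not evidence of a wrong count.

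**What to change.** In Protocol 4.1.3, open the closing sentence with an exception for VTE meeting the criteria above.

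If the protocol is not amended again, put the counting rule in SAP 8.2. For participants under Amendment 3, count as a DLT, irrespective of attribution, every Grade 2 VTE needing systemic anticoagulation and every VTE of Grade 3 or above with onset inside the VTE window. Define that window as 8 weeks with the ± 1 week resolved to one stated cutoff day, or until study discontinuation if sooner. Both the anticoagulation condition and the time limit must be written in, or the rule will over-count.

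For Table 3.22 and Listing 22, state that the Determinative Period is 21 days for general DLTs and that same window for VTE.

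The cost is one clause or one SAP paragraph, plus one definition. No new data or procedures are needed. The downside is that the reported DLT rate may be slightly higher.

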Nausea	
 • Grade 3 persisting >3 days despite BSC^a
Vomiting	
 • Grade 3 or 4 persisting > 3 days despite BSC^a
Diarrhea	
 • Grade 3 or 4 persisting > 3 days despite BSC^a
Fatigue	
 • Grade 3 persisting > 5 days
Hypertension	
 • Grade 3 that cannot be controlled with medical therapy • Grade 4
ECG-change	
 • > 20 msec extension of the QRS-interval compared to baseline
Laboratory abnormality	
 • Grade 3 persisting > 3 days despite BSC^a • Grade 4
Any other	
 • Grade 2 leading to frequent dose interruptions despite BSC^a and limiting GSK3368715 dosing to <80% of expected dose • Grade 2 requiring delay of GSK3368715 administration for > 14 days • Grade \geq3

DLT criteria for Hematologic Toxicity	
Neutropenia	
 Grade 3 persisting > 3 days despite BSC^a Febrile neutropenia Grade 4
Thrombocytopenia	
 Grade 3 persisting > 3 days despite BSC^a Grade 3 associated with clinically significant hemorrhage Grade 4
Any other ^b	
 Grade 2 and 3 leading to frequent dose interruptions despite BSC^a and limiting GSK3368715 dosing to < 80% of expected dose Grade 3 persisting > 3 days despite BSC^a Grade 4
Venous Thromboembolism	
 Grade 2 venous thromboembolism (VTE) that requires systemic anticoagulation or VTE Grade ≥ 3 during the first 8 (± 1) weeks or until study discontinuation (e.g., disease progression), whichever occurs sooner.

ALT=alanine aminotransferase; AST=aspartate aminotransferase; BSC=best supportive care; DLT=dose-limiting toxicity; ECG=electrocardiogram; ULN=upper limit of normal

- a. Best supportive care if available, according to institutional standards
b. With the exception of lymphocytopenia

For participants who experience a toxicity that meets the criteria of DLT, administration of GSK3368715 will be held pending management and resolution of the toxicity.

Participants who withdraw from the study before completing 21 days of intervention for reasons other than DLT may be replaced at the discretion of the sponsor.

Guidance for the management of toxicity, including dose modification algorithms, is provided in [Appendix 12](#).

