1. Details of liver chemistry stopping criteria and required actions and follow-up assessments after liver stopping or monitoring event are given in Section 7.1 and Appendix 7 All events of ALT $\geq 3 \times$ upper limit of normal (ULN) and bilirubin $\geq 2 \times$ ULN (>35% direct bilirubin) or ALT $\geq 3 \times$ ULN and international normalized ratio (INR) >1.5, if INR measured, which may indicate severe liver injury (possible Hy's Law), must be reported as an SAE (excluding studies of hepatic impairment or cirrhosis).
2. Local urine testing will be standard for the protocol unless serum testing is required by local regulation or IRB/IEC.

10.3. Appendix 3: Adverse Events: Definitions and Procedures for Recording, Evaluating, Follow-up, and Reporting

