
1. Serum bilirubin fractionation should be performed if testing is available. If serum bilirubin fractionation is not immediately available, discontinue study intervention for that participant if ALT \geq 3xULN **and** bilirubin \geq 2xULN. Additionally, if serum bilirubin fractionation testing is unavailable, **record presence of detectable urinary bilirubin on dipstick**, indicating direct bilirubin elevations and suggesting liver injury.
2. All events of ALT \geq 3xULN **and** bilirubin \geq 2xULN (>35% direct bilirubin) or ALT \geq 3xULN **and** INR>1.5, if INR measured which may indicate severe liver injury (possible 'Hy's Law'), **must be reported as an SAE (excluding studies of hepatic impairment or cirrhosis)**; INR measurement is not required and the threshold value stated will not apply to participants receiving anticoagulants
3. New or worsening symptoms believed to be related to liver injury (such as fatigue, nausea, vomiting, right upper quadrant pain or tenderness, or jaundice) or believed to be related to hypersensitivity (such as fever, rash or eosinophilia)
4. Includes: Hepatitis A IgM antibody; Hepatitis B surface antigen and Hepatitis B Core Antibody (IgM); Hepatitis C RNA; Cytomegalovirus IgM antibody; Epstein-Barr viral capsid antigen IgM antibody (or if unavailable, obtain heterophile antibody or monospot testing); Hepatitis E IgM antibody
5. If hepatitis delta antibody assay cannot be performed, it can be replaced with a PCR of hepatitis D RNA virus (where needed) [Le Gal, 2005](#)].
6. PK sample may not be required for participants known to be receiving placebo or non-GSK comparator interventions.) Record the date/time of the PK blood sample draw and the date/time of the last dose of study intervention prior to blood sample draw on the CRF. If the date or time of the last dose is unclear, provide the participant's best approximation. If the date/time of the last dose cannot be approximated OR a PK sample cannot be collected in the time period indicated above, do not obtain a PK sample. Instructions for sample handling and shipping are in the SRM.

Phase I Oncology liver chemistry increased monitoring criteria with continued therapy

Liver Chemistry Increased Monitoring Criteria – Liver Monitoring Event	
Criteria	Actions

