
Participant with entry criteria ALT\leq2.5x ULN ALT \geq3xULN but $<$5xULN and bilirubin $<$2xULN, without symptoms believed to be related to liver injury or hypersensitivity and who can be monitored weekly for 4 weeks
 
Participant with documented liver metastases/tumor infiltration at baseline AND entry criteria ALT$>$2.5 x ULN but \leq 5 x ULN ALT \geq3x ULN and 1.5x baseline value but ALT $<$5x ULN and 2x baseline value and bilirubin $<$2xULN, without symptoms believed to be related to liver injury, or hypersensitivity and who can be monitored weekly for 4 weeks
	
 • Notify the GSK medical monitor within 24 hours of learning of the abnormality to discuss participant safety. • Participant can continue study intervention • Participant must return weekly for repeat liver chemistries (ALT, AST, alkaline phosphatase, bilirubin) until they resolve, stabilise or return to within baseline • If at any time participant meets the liver chemistry stopping criteria, proceed as described above 
For participants with entry criteria ALT\leq2.5 x ULN
 
 • If, after 4 weeks of monitoring, ALT $<$3xULN and bilirubin $<$2xULN, monitor participants twice monthly until liver chemistries normalize or return to within baseline. 
For participants with documented liver metastases/tumor infiltration at baseline AND entry criteria ALT$>$2.5 x ULN but \leq 5 x ULN
 
 • If, after 4 weeks of monitoring, ALT $<$3xULN and $<$1.5x baseline value, and bilirubin $<$2xULN, monitor participants twice monthly until liver chemistries normalize or return to within baseline

References

10.7. Appendix 7: Medical Device Incidents: Definition and Procedures for Recording, Evaluating, Follow-up, and Reporting

There are no medical devices used in this protocol.

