	If ≥ 60 msec change from baseline occurs OR QTcF ≥ 500 msec (average of three ECGs over at least 15 minutes)	Discontinue GSK3368715 and notify the GSK Medical Monitor.
Liver		Refer to procedures outlined in Section 7.1.1 Liver Safety Required Actions and Follow up Assessments
Diarrhea	Grade 1	Initiate supportive care including loperamide.
	Grade 2	
 Initiate supportive care including loperamide. Consider hold of GSK3368715 Discuss with GSK Medical Monitor.
	Grade 3	
 Treat as above plus consider intravenous (IV) hydration, hospital admission and prophylactic antibiotics as appropriate. Hold GSK3368715 Discuss with GSK Medical Monitor. Re-start GSK3368715 at a reduced dose Discontinue GSK3368715 if not resolved to Grade ≤ 1 within ≤ 14 days
	Grade 4	
 Above plus consider intravenous (IV) hydration, hospital admission and prophylactic antibiotics as appropriate. Discontinue GSK3368715

Toxicity	Dose Adjustment/ Stopping Criteria	Management Guidelines
Nausea/Vomiting	Grade 1	
 Initiate supportive care with antiemetics as necessary.
	Grade 2	
 Initiate supportive care with antiemetics as necessary Consider hold of GSK3368715 until resolved to Grade \leq 1 within \leq 14 days Discuss with GSK medical monitor
	Grade 3	
 Supportive care as above, plus consider intravenous (IV) hydration, hospital admission and IV nutrition as appropriate. Hold GSK3368715 until resolved to Grade \leq 1 within \leq 14 days Discuss with GSK Medical Monitor. Re-start GSK3368715 at same dose if resolved within \leq 2 days Re-start GSK3368715 at reduced dose if resolved $>$ 2 days Discontinue GSK3368715 if not resolved to Grade \leq 1 within \leq 14 days
	Grade 4	
 Supportive care as above, plus consider intravenous (IV) hydration, hospital admission and IV nutrition as appropriate Discontinue GSK3368715 if lasting $>$2 days despite supportive care
All Other Toxicity*	Grade 1	
 Continue dosing with no change
	Grade 2	
 Continue dosing with no change 
OR
 
 Hold GSK3368715 for up to 1 week for toxicity to be $<$ Grade 2, then continue at the same dose (dose reduction is required if the grade 2 toxicity is considered a DLT)

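### Appendix 2 and Appendix 6 state the same mandatory ALT-plus-INR SAE rule, but only Appendix 6 exempts anticoagulated participants; the Table 6 DLT criterion also lacks the exemption

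*Protocol*

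**What the plan says.** The protocol uses the combination of ALT ≥3xULN and INR above 1.5 in three places.

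- **Section 4.1.3, Table 6 (AST or ALT row).** ALT at or above "3xULN and INR >1.5, if INR measured" is a DLT criterion. The two table footnotes deal with best supportive care and lymphocytopenia; neither mentions anticoagulants. After a DLT, "administration of GSK3368715 will be held pending management and resolution of the toxicity".
- **Appendix 2, Table 11, note 1.** ALT ≥3xULN with "international normalized ratio (INR) >1.5, if INR measured, which may indicate severe liver injury" has to be reported as an SAE. The only exclusion is for studies of hepatic impairment or cirrhosis. For the liver criteria and actions the note says that details "after liver stopping or monitoring event are given in Section 7.1 and Appendix 7".
- **Appendix 6, INR stopping limb and footnote 2.** The footnote repeats the Appendix 2 SAE rule almost word for word and then adds: "INR measurement is not required and the threshold value stated will not apply to participants receiving anticoagulants".

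Other provisions bear on who can be affected. Section 6.7 permits prophylactic low molecular weight heparin and oral Factor Xa inhibitors; Section 6.7.1 prohibits vitamin K antagonists. Inclusion criterion 3 (Section 5.1) waives the PT/INR and PTT entry limit for participants on systemic anticoagulation. Schedule of Activities Table 2 draws coagulation tests on Days 1, 8, 15 and 22, weekly afterwards, and at treatment discontinuation.

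**The concern.** The two SAE statements are the same rule, once with the exemption and once without, so a difference in purpose does not explain the gap. A site following Appendix 2 reports the event as an SAE; a site following Appendix 6 need not. The pointer that should lead from Appendix 2 to the fuller text goes to Appendix 7, where the content is "There are no medical devices used in this protocol".

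The DLT side is a separate and softer matter. The protocol waives the INR entry limit for anticoagulated participants and switches off the INR threshold for them in Appendix 6. In effect it accepts that INR does not indicate liver function in this group. Table 6 nevertheless lets that INR complete a DLT criterion.

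At stake is how a case is classified in the final report. DLT incidence is a Part 1 primary endpoint (Protocol Section 3), and SAEs are summarised in SAP Table 3.6.

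**Working it through.** The plan gives no figure to reproduce. The check is a comparison of texts, followed by one small piece of arithmetic.

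**1. Can the case arise?** Anticoagulants are permitted (Section 6.7), the entry INR limit is waived for those taking them (Section 5.1), and restart after a VTE requires adequate anticoagulation (Appendix 12, Table 14). INR is scheduled, so the condition that it be measured is normally met. The ±3 day window from Day 8 onward means that the Day 22 draw can also fall inside the 21-day DLT period. The documents do not say whether the permitted agents raise INR above 1.5; that is an assumption.

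**2. Apply each rule to one case.** A participant on a Factor Xa inhibitor, within the first 21 days, has ALT 3.5xULN, INR 1.7, bilirubin <2xULN and no symptoms, and can be monitored weekly. ALT is set below 5xULN because at or above that level it is by itself a DLT criterion and a stopping event.

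| Rule | Condition that comes first | Result |
|---|---|---|
| Appendix 2, note 1 | Must be an AE: clinically significant in the investigator's judgement (Appendix 3, 10.3.1 and 10.3.2) | SAE report mandatory |
| Appendix 6, footnote 2 | Same | INR threshold switched off; no SAE through this rule |
| Appendix 6, stopping and monitoring | None further | Not a stopping event; a monitoring event: "Participant can continue study intervention" |
| Table 6 | Investigator finds it relevant and at least possibly drug-related (Section 4.1.3) | If so, DLT and hold |

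The first two rows contradict each other. The last two do not: one defines a DLT and the other defines liver stopping and monitoring.

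**3. Does a cross-reference resolve it?** Appendix 2 names Section 7.1 as well as Appendix 7, and Section 7.1.1 leads to Appendix 6. The exemption can therefore be reached, but nothing says which of the two SAE sentences prevails. For DLT management, the liver row of Table 14 says: "Refer to procedures outlined in Section 7.1.1 Liver Safety Required Actions and Follow up Assessments". That governs actions and does not remove a DLT already counted.

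**4. What would one case change?** Section 4.1.1 allows 3 to 12 DLT-evaluable participants at a dose. With no other DLT, one such case moves reported incidence from 0 to 1/3 = 33.3%, 1/6 = 16.7% or 1/12 = 8.3%. The SAE summary changes by one participant. This is the effect of a single case if it occurs, not a forecast.

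**5. Would a reader see it?** SAP Table 1 places PT/INR under Coagulation. The final out-of-range listings (24 and 25) cover chemistry and haematology, and Listing 26 covers character results. No final display in SAP Appendix 10 is specified to show numeric INR.

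**The case against.** The strongest reply is that this is a drafting slip with little consequence, and several parts of it stand.

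- **Only one DLT definition exists.** A reader might infer that DLT status is decided two ways. It is not: Appendix 6 never defines a DLT, and an event may be a DLT without being a stopping event. Table 6 also differs from Appendix 6 elsewhere (it adds AST and omits the limb for participants who cannot be monitored), so the omission could be deliberate, though the text does not say so.
- **The dosing instructions are compatible.** Appendix 6 permits continuation and does not require it, so holding drug satisfies both sections.
- **Judgement comes first.** An abnormal result must qualify as an AE before it can be an SAE, and a DLT needs relevance and attribution. Both narrow the point. Neither is a written exemption: an ALT rise judged possibly drug-related passes, whatever raised the INR.
- **Over-reporting breaks no rule.** Sending an SAE report under Appendix 2 does not breach Appendix 6. The sections still disagree on whether the report is mandatory.
- **Some displays help.** The dose-escalation listing of abnormal laboratory tests in SAP 3.1.1.1 may show INR. Final Listings 8, 18, 22 and 24 give concomitant medication, reasons for seriousness, DLTs and ALT. What is missing from the final set is the INR value.
- **The exposed group is small.** Warfarin is prohibited. Khorana score ≥3 and prior VTE are excluded (Section 5.2, criterion 16). Enrolment was to resume in the PK/PD cohorts, where an on-treatment biopsy is required (Table 3) and INR must be normal within the preceding 48 hours (Section 8.7.3).

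**Conclusion.** The point holds and is minor. Appendix 2 note 1 and Appendix 6 footnote 2 contradict each other on whether an anticoagulated participant meeting only the ALT-plus-INR limb is a mandatory SAE, once the investigator regards the event as a clinically significant AE. The Appendix 2 cross-reference to Appendix 7 is wrong. Separately, Table 6 lets an anticoagulant-driven INR complete a DLT criterion, which sits badly with how the protocol treats INR in this group elsewhere.

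The practical case rests on the assumption that a permitted agent can raise INR above 1.5. The documents give no rate of anticoagulant use, of ALT 3 to <5xULN or of raised INR, so no expected number of cases is offered.

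A reader might infer that dose recommendations were affected. The documents do not support that: the model prior and the DLT counts by dose are not available in them, and SAP 2.1 states that enrolment has ended and no RP2D analysis will be run. What remains is classification in the final displays.

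**What to change.** 1. Add the Appendix 6 footnote 2 exemption to Appendix 2 note 1 and to the INR limb of Table 6.
2. In Appendix 2 note 1, change Appendix 7 to Appendix 6.
3. Leave DLTs and SAEs already recorded as they were classified.
4. In SAP Listing 22, flag any DLT met only through ALT plus INR while the participant was on an anticoagulant, and show the INR value.

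The cost is two footnotes, one corrected reference and one flag in an existing listing. The downside is that such a case would no longer count as a DLT through this limb. The ALT ≥5xULN, bilirubin, symptom and persistence limbs remain. With enrolment ended, the Table 6 wording will affect few if any new cases; the listing flag is the part that can still inform the final report.
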